^k All standard digital ECGs will be performed before dosing and after the subject has been supine for at least 5 minutes. At the Week 1, Week 2, Week 17, and Week 18 Visits, ECGs will be collected before dosing and at 1.5, 3, 4, and 6 hours after the morning dose. At the Week 1, Week 2, Week 17, and Week 18 visits the 4-hour postdose ECG will be collected before the 4-hour postdose spirometry assessment. The predose ECGs collected at the Week 1 (Day 1) visit will be performed in triplicate. If study drug is not administered on the day of the visit (i.e., because of study drug interruption or permanent discontinuation of study drug), only 1 ECG will be collected.

^l Vital signs and pulse oximetry will be collected before dosing and after the subject has been at rest (seated or supine) for at least 5 minutes.

^m At all visits, spirometry must be performed for all subjects before dosing and should be performed prebronchodilator ([Section 11.6.1](#)). At Week 1, Week 2, Week 17, and Week 18, subjects < 18 years of age at the Screening Visit will have additional spirometry performed at 2 and 4 hours after the morning dose. If more than 1 spirometry assessment is required at a visit, bronchodilators will be withheld until completion of the last scheduled spirometry assessment is completed.

ⁿ The Sweat collection on dosing visits should occur approximately 1 hour before the PK sample collection and before the morning dose of the study drugs. Sweat collection will not overlap with any other study assessments ([Section 11.6.2](#)).

Table 3-2 Treatment Periods, Washout Period, ETT, and Safety Follow-up Visit Assessments – Study VX14-661-108

Event/Assessment ^b	Treatment Period 1				Washout ^a	Treatment Period 2				ETT Visit ^c	Safety Follow-up Visit 28 days (± 7 days) After Last Dose ^d
	Week 1 (Day 1)	Week 2 (Day 15) (± 3 Days)	Week 4 (Day 29) (± 5 Days)	Week 8 (Day 57) (± 5 Days)	Safety Evaluation Visit Week 12 (Day 85) (± 5 Days)	Week 17 ^a (Day 113)	Week 18 (Day 127) (± 3 Days)	Week 20 (Day 141) (± 5 Days)	Week 24 (Day 169) (± 5 Days)		
Hematology ^o	X	X	X	X	X	X	X	X	X	X	X
Coagulation ^o	X			X	X	X			X	X	X
Serum chemistry ^o	X	X	X	X	X	X	X	X	X	X	X
Lipid panel ^p	X			X		X			X	X	
Vitamin levels (A, D, E, K, B12)	X			X		X			X	X	
[REDACTED]	[REDACTED]			[REDACTED]		[REDACTED]			[REDACTED]		
[REDACTED]	[REDACTED]	[REDACTED]	[REDACTED]	[REDACTED]		[REDACTED]	[REDACTED]	[REDACTED]	[REDACTED]		

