[REDACTED]	[REDACTED]		[REDACTED]	[REDACTED]		[REDACTED]		[REDACTED]	[REDACTED]		
PK sampling ^u			X	X				X	X	X	X
[REDACTED]		[REDACTED]									
[REDACTED]		[REDACTED]									
[REDACTED]	[REDACTED]			[REDACTED]		[REDACTED]			[REDACTED]		[REDACTED]

^o Blood samples will be collected before the first dose of study drug.

^p Subjects will require 4 hours of fasting before the blood sample for the lipid panel is obtained.

[REDACTED]

^t The samples may be collected at the study center during the study visit or may be collected by the subject at home and brought to the study visit.

^u PK blood samples will be collected pre-morning-dose at Week 4, Week 8, Week 20, and Week 24. If study drug is not administered at the visit (i.e., study drug interruption or permanent discontinuation of study drug), a PK blood sample will still be collected. At the ETT and the Safety Follow-up Visit (as applicable), a PK blood sample will also be collected.

Table 3-2 Treatment Periods, Washout Period, ETT, and Safety Follow-up Visit Assessments – Study VX14-661-108

Event/Assessment ^b	Treatment Period 1				Washout ^a	Treatment Period 2				ETT Visit ^c	Safety Follow-up Visit 28 days (± 7 days) After Last Dose ^d
	Week 1 (Day 1)	Week 2 (Day 15) (± 3 Days)	Week 4 (Day 29) (± 5 Days)	Week 8 (Day 57) (± 5 Days)	Safety Evaluation Visit Week 12 (Day 85) (± 5 Days)	Week 17 ^a (Day 113)	Week 18 (Day 127) (± 3 Days)	Week 20 (Day 141) (± 5 Days)	Week 24 (Day 169) (± 5 Days)		
	■	■	■	■	■	■	■	■	■	■	■
Randomization ^w	X										
Meal(s) or snack(s) at site ^x	X	X	X			X	X	X			
Study drug dosing ^y	X	X	X			X	X	X			
Study drug count		X	X	X			X	X	X	X	
Concomitant medications ^z	X	X	X	X	X	X	X	X	X	X	X
Concomitant treatments and procedures	X	X	X	X	X	X	X	X	X	X	X
AEs and SAEs	Continuous from signing of the ICF and assent (where applicable) through the Safety Follow-up Visit										

AE: adverse event; β-hCG: beta-human chorionic gonadotropin; CF: cystic fibrosis; CFQ-R: Cystic Fibrosis Questionnaire–Revised; DNA: deoxyribonucleic acid; ECG: electrocardiogram; ETT: Early Treatment Termination; Eval: evaluation; ICF: informed consent form; [redacted]; IWRS: interactive web response system; [redacted]; PE: physical examination; PK: pharmacokinetic; SAE: serious adverse event; [redacted].

■ [redacted]

^w Randomization must occur after all inclusion and exclusion criteria are met and before the first dose of study drug. Randomization will be done through IWRS.

Randomization may occur on Day -1.

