8 STUDY DESIGN

8.1 Overview of Study Design

This is a Phase 3, randomized, double-blind, placebo-controlled, 2-period, 3-treatment, crossover, multicenter study in subjects aged 12 years and older with CF, heterozygous for the *F508del-CFTR* mutation, and a second allele with a *CFTR* mutation predicted to have residual function. A summary of mutations predicted to have residual function is in [Section 16](#). This study is designed to evaluate (i) the efficacy and safety of VX-661 in combination with ivacaftor (VX-661/ivacaftor) and (ii) the efficacy and safety of ivacaftor monotherapy in this patient population using an incomplete block design.

The treatment regimens will be

- VX-661/ivacaftor combination treatment
 - o Morning dose: 1 tablet fixed-dose combination of VX-661 100 mg/ivacaftor 150 mg and 1 tablet ivacaftor placebo
 - o Evening dose: 1 tablet ivacaftor 150 mg
- Ivacaftor monotherapy
 - o Morning dose: 1 tablet placebo visually matched to the fixed-dose combination tablet and 1 tablet ivacaftor 150 mg
 - o Evening dose: 1 tablet ivacaftor 150 mg
- Placebo
 - o Morning dose: 1 tablet placebo visually matched to the fixed-dose combination tablet and 1 tablet placebo visually matched to ivacaftor 150 mg
 - o Evening dose: 1 tablet placebo visually matched to ivacaftor 150 mg

[figure not shown]
This study includes a Screening Period (approximately 28 days), Treatment Period 1 (8 weeks), Washout Period (8 weeks), Treatment Period 2 (8 weeks), and Safety Follow-up Visit (approximately 28 days). Approximately 204 subjects (34 per sequence) will be enrolled and stratified by age at the Screening Visit (<18 versus \geq 18 years of age), FEV₁ severity (determined during the Screening Visit; <70% versus \geq 70% predicted), and type of residual function mutation on the second *CFTR* allele (Class V non-canonical splice mutation versus Classes II to IV residual function mutation; see [Section 16](#)), and then randomized (1:1:1:1:1:1) to 1 of the 6 treatment sequences, as shown in [Figure 8-1](#). A minimum of 25% of enrolled subjects will carry a Class II to IV mutation on the second *CFTR* allele (see [Section 16](#)). Stratification of enrollment will be managed through the interactive web response system (IWRS). Enrollment into the non-canonical splice strata will be limited to no more than 75% of total enrollment.

- Sequence 1: VX-661/ivacaftor in Treatment Period 1→washout→ivacaftor monotherapy in Treatment Period 2

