9.4 Prior and Concomitant Medications

Information regarding all prior and concomitant medications, including the subject's CF medications, other medications, and herbal and naturopathic remedies administered from 28 days before the Screening Period through the Safety Follow-up Visit, if applicable, will be recorded in each subject's source documents. For subjects who are screened but are not subsequently randomized into the study, details of prior medication will only be documented in the subjects' source documents.

- Subjects must remain on a stable medication (and supplement) regimen for their CF from 28 days before Day 1 through the Safety Follow-up Visit. Stable medication regimen is defined as the current medication regimen for CF that subjects have been following for at least 28 days before Day 1. Subjects must not initiate long-term treatment with new medication from 28 days before Day 1 through the Safety Follow-up Visit unless discussed and approved by the Vertex Medical Monitor. Guidelines for stable medication regimens for CF are as follows:

- o Subjects who are taking daily inhaled tobramycin or other chronically inhaled antibiotics should remain on that regimen throughout the study.
- o Subjects who are on a stable cycled regimen of a single inhaled antibiotic should continue on this antibiotic throughout the study. The timing of the first dose of study drug should be synchronized described in [Section 8.1.2](#) and [Section 8.1.4](#).
- o Subjects who alternate 2 different antibiotics monthly should remain on the same schedule during the study. To reduce variability, the inhaled antibiotic treatment should be the same and at the same stage through the cycle at the start of each study drug Treatment Period.
- o Subjects may receive doses of prednisone up to 10 mg/day (chronically) or prednisone 60 mg qd for up to 5 days without prior approval of the Medical Monitor.
- Information about bronchodilator use during the study will be collected and documented. Subjects who are using a bronchodilator must have their spirometry assessments performed according to the guidelines provided in [Section 11.6.1](#).
- Concomitant use of medications known to prolong the QT interval should be used with caution during the study, as the effect of VX-661/ivacaftor on the QT interval has not been evaluated in a thorough QT study. Consideration should be given to obtaining an ECG when concomitant medication known to prolong the QT interval is administered.

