10.2 Administration

Study drug tablets will be administered orally. Subjects will receive the same number of tablets each day to maintain the blind. Refer to [Table 10-1](#).

Table 10-1 Study Drug Administration – Treatment Period

Treatment	Time	Drug(s) and Dose(s) Administered Route of Administration
VX-661/ivacaftor	AM	VX-661 100-mg/IVA 150-mg fixed-dose tablet IVA matching placebo tablet oral
	PM	IVA 150-mg tablet oral
Ivacaftor	AM	VX-661/IVA matching placebo tablet IVA 150-mg tablet oral
	PM	IVA 150-mg tablet oral
Placebo	AM	VX-661/IVA matching placebo tablet IVA matching placebo tablet oral
	PM	IVA matching placebo tablet oral

AM: morning; IVA: ivacaftor; PM: evening.

Study drug should be administered within 30 minutes after starting a meal with fat-containing food, such as a "standard CF" high-fat, high-calorie meal or snack, according to the following guidelines:

1. Study drugs will be administered after the start and before the end of a meal throughout each of the 2 Treatment Periods. It is recommended that the duration of each meal associated with study drug intake (i.e., breakfast and dinner/snack, as applicable) should not exceed 30 minutes.
2. Study drug should be administered q12h (\pm 2 hours). For each subject, all doses (morning and evening) of study drugs will be taken at approximately the same time each day. For example, the morning dose could be taken at 08:00 every morning and the evening dose could be taken at 20:00 every evening throughout the study.
3. At the Day 1 Visit, all subjects will be observed for 6 hours after the morning dose of the study drug.
4. The date, amount taken, and time of study drug administration, including whether food was taken with each dose, will be recorded for 2 days before PK sample collection and on the days of PK sample collection.
5. On days of scheduled visits, the morning dose of study drug will be administered at the site after predose assessments have been completed. The meal or snack will be provided by the site for the morning dose of study drug.

6. If a subject's scheduled visit is to occur in the afternoon, the following guidelines must be used:
 - o If the dose in the clinic will be within 6 hours of the subject's scheduled morning dose, the subject should withhold their morning dose of study drug, and the morning dose will be administered in the clinic.

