 - o If the dose in the clinic will be more than 6 hours after the subject's scheduled morning dose, the subject should take the morning dose at home, and the evening dose will be administered in the clinic. In this event, all assessments will be collected relative to the evening dose.
7. For visits after the Day 1 Visit, subjects will be instructed to bring all used and unused study drug to the site; study drug will be dispensed at each visit, as appropriate.
8. At the Week 8 Visit, the morning dose of study drug will NOT be administered. The last dose of study drug will be the evening dose administered the day before the Week 8 Visit.
9. At the Week 24 Visit, the morning dose of study drug will NOT be administered. The last dose of study drug will be the evening dose administered the day before the Week 24 Visit.

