11.6 Efficacy

11.6.1 Spirometry

Spirometry will be performed according to the ATS/ERS guidelines²⁹ at the time points noted in [Table 3-1](#) and [Table 3-2](#) according to the additional guidelines that follow.

Prebronchodilator spirometry is defined as spirometry testing performed for subjects who have

- withheld their short-acting bronchodilators (e.g., albuterol) or anticholinergic (e.g., ipratropium bromide [Atrovent[®]]) for more than 4 hours before the spirometry assessment
- withheld their long-acting bronchodilator (e.g., salmeterol) for more than 12 hours before the spirometry assessment; and
- withheld their once-daily, long-acting bronchodilator (e.g., tiotropium bromide [Spiriva[®]]) for more than 24 hours before the spirometry assessment

During the Treatment Periods, spirometry assessments must be performed before dosing. In adolescent subjects (< 18 years of age at the Screening Visit), additional postdose spirometry assessments on Day 1 of each Treatment Period (Week 1 and Week 17) and Day 15 of each Treatment Period (Week 2 and Week 18) will be collected at 2 and 4 hours after the morning dose. A window of ± 15 minutes will be allowed around the nominal times for all postdose spirometry assessments.

During the Screening Period, spirometry assessments may be performed pre- or post-bronchodilators. At all the other visits, all spirometry assessments should be performed “prebronchodilator.”

In the event that a subject forgets to withhold bronchodilator(s), spirometry should be performed according to the following:

- If a subject’s Day 1 (Treatment Period 1) spirometry is prebronchodilator, but, on a subsequent visit, the subject does not withhold bronchodilator use, a postbronchodilator spirometry will be obtained for that visit only, and the visit will not be rescheduled.

- If, on Day 1 (Treatment Period 1), the subject does not withhold his/her dose of bronchodilator, spirometry should be performed postbronchodilator, and all subsequent spirometric measurements (according to the schedule of assessments detailed in [Table 3-2](#)) should be performed postbronchodilator.
- For visits with postdose spirometry assessments (Weeks 1, 2, 17, and 18), if the predose spirometry is performed postbronchodilator, the subject should withhold any further bronchodilator use until completion of the 4-hour postdose spirometry assessment on that day.

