#### 8.4.6 Postdose Spirometry

For the 2-hour and 4-hour postdose measurements on Day 1 and Day 15 of each treatment period, a summary of raw values for ppFEV1 will be provided by treatment group at each time point. The absolute change from the predose value of ppFEV1 on the same day will be provided by treatment at each time point. In addition, a box plot by study day and treatment group will be provided for each time point. The above analyses will be repeated for FEV1.

In addition, the number and percentage of subjects with (i) ppFEV1 decline ≥10, ≥15, and ≥20 percentage points in the absolute change from the predose value (ii) FEV1 decline of ≥0.2 L will be summarized by treatment group and by assessment day and time.

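### Protocol 10.2 item 6 contradicts the morning-dose timing of the postdose ECGs and adolescent spirometry: at a late Week 2 or Week 18 visit the series would follow a dose without VX-661, and the SAP would not separate it

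*Protocol*

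**What the plan says.** VX-661 is given once daily, in the morning fixed-dose tablet. The combination regimen in Protocol 8.1 continues: "Evening dose: 1 tablet ivacaftor 150 mg". Table 10-1 agrees, and the ivacaftor arm takes the same evening tablet.

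At Weeks 1, 2, 17 and 18, Table 3-2 footnote k states that "ECGs will be collected before dosing and at 1.5, 3, 4, and 6 hours after the morning dose". For subjects under 18 at screening, Protocol 11.6.1 states that additional spirometry "will be collected at 2 and 4 hours after the morning dose", and footnote m agrees. Footnote y and 10.2 item 5 have the morning dose given at the site on visit days.

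Item 6 of 10.2 is mandatory for afternoon visits and has two branches. If the clinic dose falls within 6 hours of the scheduled morning dose, "the subject should withhold their morning dose of study drug, and the morning dose will be administered in the clinic". If it falls later than that, the morning dose is taken at home and the evening dose is given in clinic: "In this event, all assessments will be collected relative to the evening dose". No exception is made for visits with a postdose series.

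SAP 8.4.6 begins "For the 2-hour and 4-hour postdose measurements on Day 1 and Day 15 of each treatment period" and summarises values and same-day changes by treatment and time point. SAP 8.4.3 summarises ECGs at each scheduled time point. SAP 10.2 assigns the Day 15 ECG and spirometry records by nominal visit. None of these distinguishes a series timed from a morning dose from one timed from an evening dose.

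**The concern.** A site running a Week 2 or Week 18 visit under the second branch cannot follow both instructions. If it follows item 6, the series in the combination arm is timed from a tablet without VX-661.

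The data concerned were requested for safety reasons. Protocol 8.2.4 says the adolescent postdose spirometry was added at a regulator's request. Protocol 9.4 says that "the effect of VX-661/ivacaftor on the QT interval has not been evaluated in a thorough QT study". Weeks 2 and 18 are also the only scheduled postdose series under repeated dosing.

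Spirometry is the more exposed of the two. Protocol 12.3.4.6.2 and SAP 8.4.6 analyse the change from the same day's predose value, including falls of at least 10, 15 and 20 percentage points. Under the second branch the predose reading is itself more than 6 hours after VX-661, and the later readings follow ivacaftor alone. An acute fall soon after taking VX-661 could occur before the reference reading and would not show as a change from it.

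Affected records may also be hard to find later. Item 4 of 10.2 requires dose times around PK sampling, and the visible schedule has no PK sampling at Weeks 2 or 18.

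**Working it through.** The documents give no figure to reproduce, so the check compares the passages and computes times.

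**Which visits can be affected.** The first dose of each period is given at the Day 1 and Week 17 visits (Protocol 8.1.2, 8.1.4). No home dose precedes it in that period, and Day 1 requires 6 hours of observation after the morning dose (10.2 item 3). That leaves Weeks 2 and 18, second branch only. The first branch keeps the morning dose as the reference.

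**Time since VX-661 intake.** Inputs: ECGs at 1.5, 3, 4 and 6 h and spirometry at 2 and 4 h (footnotes k and m); a gap of more than 6 h between the morning and evening doses (item 6), or 10 to 14 h if q12h (± 2 hours) is also kept (item 2). Time since VX-661 = gap + nominal time.

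| Gap between doses | ECG, h after VX-661 | Spirometry, h after VX-661 |
|---|---|---|
| Schedule (morning dose in clinic) | 1.5, 3, 4, 6 | 2, 4 |
| Just over 6 h | just over 7.5, 9, 10, 12 | just over 8, 10 |
| 10 h | 11.5, 13, 14, 16 | 12, 14 |
| 12 h | 13.5, 15, 16, 18 | 14, 16 |
| 14 h | 15.5, 17, 18, 20 | 16, 18 |

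The windows do not overlap: the earliest evening-timed ECG comes later after VX-661 than the last scheduled one (more than 7.5 h against 6 h).

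**VX-661 still present.** Input: a terminal half-life of about 116 h (Protocol 8.2.2). Assumption: simple one-compartment decay, with absorption ignored.

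- Fraction of one dose left at t hours = 2^(−t/116): 95.6% at 7.5 h, 93.1% at 12 h, 88.7% at 20 h.
- Fraction of steady state reached after 14 days = 1 − 2^(−336/116) = 0.866, about 87%.
- Accumulation with once-daily dosing = 1/(1 − 2^(−24/116)) = about 7.5-fold.

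The Day 15 ECGs are therefore taken under substantial VX-661 exposure in either case. What changes is the position relative to intake.

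**Related conflicts in item 6.**

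- Dose interval: q12h (± 2 hours) allows 12 − 2 = 10 h to 12 + 2 = 14 h. Item 6 read alone allows any gap above 6 h, so gaps between 6 and 10 h fall outside it.
- PK: footnote u states that "PK blood samples will be collected pre-morning-dose at Week 4, Week 8, Week 20, and Week 24". At a second-branch visit in Week 4 or 20, a sample timed to the evening dose is not a pre-morning-dose sample.

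**The case against.** The strongest reply is that the situation will seldom arise. The default is a morning dose at the site, the visit-specific footnotes already name the morning dose, and the first branch covers many afternoon visits. With the protocol's own example of an 08:00 dose, a gap just over 6 h puts the 6-hour ECG just after 20:00. A 10 h gap puts it at 08:00 + 10 h + 6 h = midnight. This stands: the count is probably small, and the documents give no frequency.

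A reader might go further and infer that the combination's QT safety is not measured at these visits, or that the two active arms are compared on ivacaftor alone. The documents do not support that. By Day 15 VX-661 has accumulated, most of the last dose remains, and SAP 8.4.3 takes ECG change from the period baseline rather than from the same day's predose reading. A reader might also infer that a VX-661 effect is diluted in proportion to the share of affected visits, or that its peak is missed. The first assumes no VX-661 effect beyond 7.5 h and needs a frequency. The second needs a time of peak concentration. The documents give neither.

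The side points are also limited. Item 6 does not suspend item 2, so a site may apply both. Dose and sample times are recorded on PK days and the analysis is a population model, so an off-schedule PK sample remains usable.

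Safety analysis is descriptive, with no testing, so no hypothesis test is affected. None of this removes the contradiction, and it does not answer the point on same-day spirometry change, where the reference reading itself moves.

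**Conclusion.** The contradiction is real and limited. Item 6, second branch, and footnotes k and m with Section 11.6.1 name different reference doses for the same Week 2 and Week 18 assessments, and the SAP would combine the results under one label.

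- **Adolescent spirometry:** in an affected visit the same-day change, with its 10, 15 and 20 point thresholds, describes the hours after an ivacaftor-only tablet and does not describe the response to taking VX-661.
- **ECGs:** the readings remain valid on-treatment data for the combination, but they fall more than 7.5 h to more than 12 h after VX-661 intake instead of 1.5 to 6 h. They do not belong under the same postdose time point.
- **First-dose series at Weeks 1 and 17:** not affected.

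The time windows follow from the documents' own figures. The statement that VX-661 is still present rests on the 116 h half-life and simple decay. The effect on any summary cannot be sized. The point still merits correction before the data are summarised: the mixing would be silent, it concerns safety data, and the visible text does not ensure that affected records can be identified afterwards.

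**What to change.** **Protocol.** The sponsor must reconcile 10.2 item 6 with Table 3-2 footnotes k, m and u, Section 11.6.1 and q12h (± 2 hours), and state which governs. This review does not choose the visit or dosing rule. At Weeks 2 and 18, record whether the reference dose was the morning or the evening dose, and its time.

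**SAP 8.4.6.** Summarise or list evening-timed postdose spirometry separately from the morning-dose postdose summaries, including the decline counts.

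**SAP 8.4.3.** Flag evening-timed ECGs and leave them out of the by-time-point postdose summaries. Retain them in the threshold summaries over the whole treatment-emergent period, because they are genuine on-treatment readings.

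**Cost.** One protocol clarification, one extra recorded field, one derivation rule, and slightly fewer records in the postdose tables.
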